**Corresponding author:**

[name], Associate Professor

School of Rehabilitation Therapy, Queen's University, [name]

[[contact]](mailto:[contact])

**Version date:** November 20, 2025

**Results:** Our internal pilot cluster randomized trial was registered prospectively in February 2023 (NCT05736133). Recruitment of primary care sites (clusters) was completed in June 2023 and cluster randomization was performed in July 2023. Patient recruitment began in October 2023. When progression criteria for patient participant recruitment rate, assessment completion rate, and treatment fidelity were met at the 20-week time-point; the decision was made to progress directly into the fully powered trial without performing any preliminary analysis of the outcome data collected during the pilot phase with the plan to incorporate this data in the full trial analysis. The fully powered trial was registered at ClinicalTrials.gov (NCT06358521) at the end of the pilot phase (April 2024). Participant recruitment was completed in November 2024. At the time of publishing this protocol and analysis plan, data collection is ongoing and expected to be completed by December 19, 2025. Analysis will be conducted as outlined in this pre-specified analysis plan starting after all data collection is complete. No interim analysis was planned or completed. The findings are anticipated to be published in 2026.

## Introduction

Hip and knee pain are leading contributors to reduced functioning. Osteoarthritis (OA) alone is one of the leading causes of pain, disability, and reduced quality of life in patients, and the hip and knee are the most common body regions. Arthritis currently affects one in five Canadians, and this is expected to rise to nine million people by 2040^2. OA places a substantial burden on society in terms of both direct and indirect costs, including reduced work productivity and missed work.

Hip and knee pain and other musculoskeletal (MSK) conditions are among the most common reasons for a patient to access primary care. Due to the rise in patients seeking support at the primary care level for many chronic conditions and a growing shortage of primary care providers, patients often do not receive timely access to the care they require. Additionally, for patients without primary care providers, their first point of contact for their pain is often the emergency department (ED), which contributes to long wait times and overcrowding of the EDs.

There is an urgent need for evidence-informed and patient-centred interprofessional primary care models to meet the needs of patients with hip and knee pain. In Canada, federal and provincial governments have identified that interprofessional teams with complementary skillsets are required to address patients' multiple needs and to improve the effectiveness, efficiency, and sustainability of the healthcare system. Research from other health conditions suggests that team-based primary care can improve access to appropriate care, coordination of care, and patient outcomes. One example of such an integrated model of care is having a physiotherapist (PT) integrated within primary care teams and available as the first point of contact (PT-led primary care). Physiotherapists can provide comprehensive and efficient management of patients seeking primary care for musculoskeletal conditions such as hip and knee pain, and evidence suggests that PTs are able to provide collaborative care in a primary care setting.

Previous studies on PTs working in primary care for MSK disorders have demonstrated that PTs provide equal or improved care compared to physicians or nurse practitioners (NPs) and that patient satisfaction is high when being managed by a PT. Studies conducted in the UK concluded that PTs working in primary care resulted in freeing up primary care practitioners' time, reduced referrals to secondary and tertiary care, fewer requests for diagnostic imaging, increased patient satisfaction, and potential for cost savings.

The impact of a PT-led primary care model for patients with hip and knee pain has not been examined in the Canadian context. High quality evidence is needed to assess the effects of the PT-led primary care model on the following: patient health outcomes; access to care; health service utilization; and society (e.g. occupational productivity, costs). Additionally, there is a need to assess how this model of care is implemented, potential mechanisms of the model, and patients' experiences with the model of care.

The goal of publishing this protocol and analysis plan for our cluster trial and embedded process evaluation is to transparently communicate our design and methods in enough detail to be reproduced and to communicate the analytic plan in advance of analysis to reduce risk of analytic or reporting bias.

## Research Objectives:

- 1) To determine the effectiveness of a PT-led primary care model for people with hip and knee pain at

improving function (primary outcome), pain intensity, quality of life, global rating of change, patient satisfaction, and adverse events compared to usual physician-led primary care, when evaluated over a one-year period from the initial consultation.

2) To assess the impact of a PT-led primary care model for patients with hip and knee pain on the health system and society (healthcare access, primary care physician workload, healthcare utilization, missed work, cost-effectiveness), evaluated over a one-year period from initial consultation.

## Methods

**Design:** The trial is a parallel arm cluster randomized controlled trial (RCT) conducted across 14 primary care sites in Ontario, Canada. Participating sites were randomized 1:1 to either a PT-led primary care model or the usual physician-led primary care model for hip and knee pain. Randomizing at the practice level, rather than the patient level, enabled full integration of PTs within the primary care team and minimized the risk of contamination between providers. This protocol and analysis plan is according to the Standard Protocol Items: Recommendations for Interventional Trial (SPIRIT) reporting guidelines. See Table 1 for an overview of the schedule of enrolment, interventions and assessments as recommended in the SPIRIT guidelines.

Table 1. Schedule of enrolment, interventions, and assessments.

	STUDY PERIOD						
	Enrolment or clusters	Allocation of clusters	Enrolment of patient participants	Post-allocation			Close-out
TIMEPOINT	Pre-intervention	Pre-intervention	0 (baseline)	3 mo.	6 mo.	9 mo.	12 mo.
ENROLMENT OF PRIMARY CARE SITES:							
Eligibility screen	X						
Informed consent	X						
Allocation to study group		X					
ENROLMENT OF PATIENT PARTICIPANTS:							
Eligibility screen			X				
Informed consent			X				
INTERVENTIONS:							
PT-led primary care				◆	—————→		
Usual care				◆	—————→		
ASSESSMENTS:							

Participant characteristics and demographic information			X				
Participant health and experiences outcomes (LEFS, pain intensity, EQ-5D-5L, PSEQ, PCS, TSK-11, PHQ-2)			X	X	X	X	X
Participant health and experiences outcomes (GROC, satisfaction, adverse events)				X	X	X	X
Health system and societal outcomes (provider encounters, EHR utilization, healthcare utilization, missed occupational activities, assistance required)				X	X	X	X
Implementation measures (timely access, PT as first point of contact, access to PT, hip/knee management)			X	X	X	X	X
Implementation measures (patient adherence)				X			
QUALITATIVE INVERVIEWS:							
Patient participants				X			

The trial includes a multi-methods process evaluation, guided by the United Kingdom Medical Research Council (MRC) framework for developing and evaluating complex interventions. The process evaluation is exploring how the intervention is being implemented, differences in primary care provided to people with hip and knee pain receive in the PT-led primary care model in comparison to the usual care model, potential mechanisms of the model of care, and experiences of patients with this model of care. This is essential for interpreting trial results; for example, understanding why the intervention may fail, yield unintended effects, or succeed — and can help guide future implementation of this model of care in the future if effective.

This cluster randomized trial is being run along-side another cluster randomized trial (clinicaltrials.gov NCT04287413) that aims to determine the impact of a PT-led primary care model for people with low back pain. The trial focused on hip and knee pain (the protocol and analysis plan presented here) is being carried out at 14 of the 20 sites participating in the low back pain trial (14 sites located in Ontario are included, six sites in BC are not included). We used the existing randomization schedule created for the low back pain trial to be able to efficiently assess the impact of a PT-led primary care model for people with hip and knee pain by leveraging the PTs and research staff already hired for the low back

pain study. The multi-methods process evaluation for the low back pain trial includes a mixed-methods exploration of how the context influences implementation of a PT-led primary care model and a qualitative exploration of the perspectives of primary care team members. These elements were intentionally not included or replicated in the process evaluation plan for the hip and knee trial in this trial. However, we anticipate findings related to the perspectives of primary care team members and contextual factors influencing implementation of the PT-led primary care model explored as part of the process evaluation in the low back pain trial will be informed by experiences implementing a PT-led primary care model for both people with low back pain and people with hip or knee pain.

The process evaluation will provide an understanding of how the PT-led primary care model for patients with hip and knee pain was implemented, explore the potential mechanisms of the interventions, and capture the experiences of patients who received care through this model.

**Patient and Public Involvement:** A person with lived experience was involved throughout this study, contributing to the conceptualizing the study, study design, and selection of outcomes important to people with lived experience. Their ongoing involvement included pre-testing data collection tools, supporting the interpretation of process evaluation results, and co-developing knowledge mobilization supports such as tailored summaries that will be distributed through patient organizations.

**Enrollment and Randomization of Sites:** We enrolled all 14 Ontario sites from the 20 sites included in our cluster-RCT testing a similar model of care for people with low back pain in Ontario and British Columbia. We used the existing randomization schedule, with a 1:1 ratio of the intervention and comparison arms. Covariate constrained randomization was used by an independent statistician to reduce the risk of baseline imbalances across study arms; the number of active patients and rural versus urban clinic setting were used as covariates. Each cluster name was concealed with a deidentified code prior to randomization. The maximum tolerable difference for rural/urban was 1. The strata balancing criteria was 10% for number of active patients.

**Strategies to Mitigate Bias:** Given the nature of the trial design and the interventions being compared, blinding was not feasible for the PTs, patient participants, primary care team members, or research assistants. While this limitation is inherent to the study design, we implemented several measures recommended for cluster randomized trials to reduce potential bias.

A common concern in cluster RCTs is the risk of selection and recruitment bias, particularly when patient enrollment occurs after cluster assignment. To address this, we took efforts to invite consecutive patients with hip or knee pain to participate in the study, to ensure RAs who handled recruitment and consent were not familiar with the patients, and to apply inclusion and exclusion criteria consistently across all sites. We also provided identical trial information to all potential participants before obtaining consent, regardless of cluster. This meant that we did not reveal which study arm participants were in until after obtaining their consent.

**Patient Participant Recruitment:** During patient participant recruitment, medical secretaries screened patients to be invited to participate when they booked an appointment for hip or knee pain. As an additional strategy, potential participants were also identified any healthcare provider (HCP) when they sought care for their hip or knee pain during a clinical visit. Potential participants who were agreeable to being invited to participate were contacted by a study research assistant (RA) to explain the details of the study. Those who were interested in participating were asked to complete a consent form that was built into the baseline surveys in a secure data collection platform (REDCap, Research Electronic Data

Capture). If a potential participant requested to do this in-person, arrangements were made to meet with the RA who provided detailed written and verbal information about the study and obtained consent for participation from those patients who were interested. A verbal consent process was in place for those who preferred to do this over the phone or in a virtual meeting.

**Inclusion/Exclusion:** All adult ( $\geq 19$  years) patients who sought primary care for their hip or knee pain of any duration at participating sites were invited to meet with the RA to discuss participating in the study. Potential participants were excluded if: they reported not being able to understand, read, and write English; they had known cancer causing their hip or knee pain; or they reported being unable to complete the scheduled follow-up surveys over the one-year study period. The inclusion criteria for primary care sites were to have at least 1,500 rostered patients and two or more family physicians. Those sites that already had physiotherapy services or not enough space to include the physiotherapist were excluded.

**Study Power:** Participants were recruited over a 13-month period at all 14 primary care sites (7 PT-led arm, 7 usual care arm). Our power calculation is based on methods described by Hemming et al. Our sample size calculation is targeted to detect a clinically meaningful mean difference of 9 points on the Lower Extremity Functional Scale (LEFS) using a two-sided alpha of 0.05, assuming a conservative standard deviation of 16, a conservative intracluster correlation coefficient of 0.1, a cluster autocorrelation coefficient of 0.5, an individual autocorrelation coefficient of 0.6, and a coefficient of variation of 0.7. Allowing for an attrition of 20% of patient participants at the 12-month follow-up, we require a sample size of 560 participants to achieve  $>80\%$  power. Pilot work for this study suggested we would recruit 1 patient per week per site; as such, we planned and prepared resources to recruit approximately 728 participants.

### **Interventions:**

**PT-Led Primary Care Model for Hip and Knee Pain:** The index intervention incorporates a PT within the primary care team as an option for the first point of contact for people presenting with hip or knee pain for one year from the time of enrolment. Patients in this model are given the choice of seeing the PT or primary care provider first. There are four key components of the PT-led intervention: 1) initial assessment and screening; 2) brief individualized intervention at first visit; 3) health services navigation; 4) and providing additional PT care for people with an unmet need (e.g., no insurance coverage for PT). **Physiotherapist training:** During two consecutive days, seven registered physiotherapists received training on this new model of care to apply across the seven sites randomized to the PT-led primary care model for hip or knee pain.

- 1) Initial assessment and screening: the PT provides a comprehensive patient assessment according to established clinical practice guidelines. The assessment includes taking a detailed clinical history; screening for potential pathology and the need to refer to another HCP; physical examination; and using a validated patient reported outcome measure (LEFS) to guide clinical decision-making.
- 2) Brief individualized intervention at first visit: the PT intervention is at the discretion of the PT to reflect real-world PT practice.
- 3) Health services navigation: where applicable, patient participants are provided with options available to them in their community for rehabilitation programs or other health or social services. For example, they may be referred to community PT for ongoing management or presented with options for group exercise programs. Patients are assessed regarding the need for specialist referrals or resources available to manage complex clinical presentations such as

comorbidity, frailty, or the need for surgical consult. Patients are referred to the primary care provider if specialized services are needed or when the PT cannot provide a direct referral. In addition, patients are referred back to their primary care provider when it is deemed that their clinical needs fall outside of the PT's scope of practice (i.e., medication advice, pathology requiring medical attention) or they identify factors that require mental health intervention.

4) Providing additional PT care: patient participants who require PT but do not have the appropriate access to community-based services are managed by the PT who provided the assessment in the primary care setting. Individuals with private or government health coverage are referred to services outside of the primary care practice when they are accessible to the patient in order to avoid duplication of available services. The amount of care provided is decided on a case-by-case basis in alignment with the health needs for each individual.

**Usual Care Model:** The physician- or nurse practitioner -led primary care intervention is unstandardized to best reflect the usual primary care clinical practice in Ontario. Patients in the usual care group are seen by either a primary care physician or a nurse practitioner as their first point of contact, depending on the current practice at the clinic. Participants in both groups are permitted to seek additional care from interprofessional team members within their primary care team or health services outside of the primary care clinic as needed.

#### **Duration of Treatment Period:**

The intervention is being carried out over a one-year period from the time of consent. All participants in the intervention arm are offered an initial assessment with the PT. While some participants in the intervention arm may be recommended to seek community health services if they have access to comprehensive health insurance, they have access to the PT as a member of their primary care team throughout the one-year follow-up period if they require additional support for their hip or knee pain. The frequency and duration of visits is determined by the PT and patient participant. The usual care model is ongoing and involves continuing as usual, and process outcomes are being collected from the date of consent to one-year post enrollment.

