#### **Data Collection and Management:**

All baseline measures have been collected from participants and follow-up data collection is ongoing. We used several approaches to support participant retention at all time points. Research assistants maintained regular contact, sending reminders every two to three days via personalized emails, phone calls, and text messages to encourage survey completion. When preferred by participants, surveys were completed in person or by phone to enhance engagement and reduce the likelihood of attrition.

All data at baseline and follow-up timepoints is being collected through online surveys using REDCap (Research Electronic Data Capture), a secure online survey and data capture tool that is hosted at Queen's University.

Electronic health record (EHR) data is being extracted by trained research assistants at the end of the one-year intervention period directly into a securely stored database to capture all primary care provided related to the hip or knee pain. Unique study identifiers are used to link responses from the surveys with data obtained in the EHRs.

At the end of the study, survey responses will be exported from REDCap into encrypted, password-protected datasets and securely stored in Microsoft OneDrive. Data extracted from the EHR, as well as the master list linking participant identifiers to study IDs, will also be kept in encrypted, password-protected files on OneDrive. Audio recordings from qualitative interviews are being transcribed, de-identified, and stored in a secure OneDrive environment at Queen's University.

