### 3. Health System Outcomes

Primary care physician or nurse practitioner visits: the total number of patient visits, both initial and follow-up, related to hip or knee pain. This metric is being used to explore whether involving PTs in care delivery helps alleviate demand on primary care providers, potentially allowing them to allocate more time to patients with other health concerns.

Healthcare utilization within the primary care team: consultations with all primary care team members (e.g., physicians, nurse practitioners, nurses, social workers, and occupational therapists), including the PT in the intervention sites, and group programming accessed within the organization. This data is being collected from the EHR abstraction process.

Healthcare utilization outside of the primary care team: medications used; walk-in clinic visits; ED visits; inpatient hospital stays; diagnostic imaging; surgeries, injections, and other interventional procedures; visits to specialist physicians; and visits to other health professionals outside the primary care team (e.g., chiropractors, massage therapists, occupational therapists, physiotherapists, chronic pain clinics). These outcomes are being collected from the self-report surveys at each follow-up assessment and verified, whenever possible, in the EHR.

Missed Occupational Activities: self-reported time lost from paid employment, volunteer, homemaking, or educational activities.

Assistance required: self-reported paid and unpaid assistance required. For example, self-care (e.g., taking medications, dressing/undressing, going to the bathroom, bathing/showering, grooming), shopping/groceries, meal preparation, housework, managing finances, or transportation (e.g., to a medical appointment).

**Costs:** Total per-person costs include both direct and indirect healthcare costs, with indirect costs estimated using a human capital approach based on time missed from work or other daily activities.

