**Implementation:**

Consistent with the UK MRC guidelines, we are collecting the following implementation measures as part of our process evaluation:

Timely access to care: determined by the percentage of patients with hip or knee pain who are assessed within 48 hours of calling for an appointment. Only participants who were invited to participate at the time of calling for an appointment for their hip or knee pain will be included in this analysis. Participants who were invited to participate at the time of an appointment with another primary care provider will not be included.

First contact care by the PT: using the percentage of patients with hip or knee pain in the PT-led primary care arm who visited a PT as their first point of contact for the current episode of hip or knee pain.

Hip and knee pain management provided: visits to the primary care site related to hip and knee pain are being collected from the EHR, along with indicators for the following process measures: education provided; exercises prescribed; psychological interventions provided; referrals made to internal primary care team members; referrals made to external HCPs; medications prescribed, deprescribed, and suggested; diagnostic imaging ordered; notes sent to employers or insurers; messages sent to internal primary care team members; and other interventions provided.

Patient adherence to recommendations: adherence to PT activity and exercise recommendations is being collected at the 3-month follow-up survey. We will also be able to determine if participants accessed community PT as part of each follow-up survey timepoint.

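### Does the unstated start date for counting physician and nurse practitioner visits undermine the workload comparison?

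*Combined protocol and SAP*

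**What the plan says.** Objective 2 (Research Objectives) covers physician workload, utilization and cost-effectiveness, "evaluated over a one-year period from initial consultation". Section 3, Health System Outcomes, defines the physician or nurse practitioner (NP) visit outcome as "the total number of patient visits, both initial and follow-up, related to hip or knee pain" and gives no dates. Duration of Treatment Period starts the intervention year at consent and adds that "process outcomes are being collected from the date of consent to one-year post enrollment". Data Collection and Management has research assistants extract the electronic health record (EHR) at the end of that year "to capture all primary care provided related to the hip or knee pain", again with no start date.

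Booking staff were the main source of recruits. As a further route, under Patient Participant Recruitment, "potential participants were also identified any healthcare provider (HCP) when they sought care for their hip or knee pain during a clinical visit"; a research assistant then made contact and consent followed. The Implementation section deals with this route for one measure only, timely access: "Participants who were invited to participate at the time of an appointment with another primary care provider will not be included".

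The Data Analysis Plan compares visits by rate ratio, accounting for clustering, and uses follow-up time as an offset in its utilization models. The same visits feed the primary-care costs.

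**The concern.** For someone recruited during a visit, that visit can precede consent. If counting starts at consent it drops out, although the outcome is said to include initial visits.

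The loss need not balance between arms. In usual care, "Patients in the usual care group are seen by either a primary care physician or a nurse practitioner as their first point of contact". In the PT-led model, "Patients in this model are given the choice of seeing the PT or primary care provider first". An omitted first visit is therefore a physician or NP visit in usual care but only sometimes in the PT-led arm. Physician and NP visits are the plan's measure of whether the model relieves primary care, so first contact is close to the heart of what is being measured. At stake would be a visit rate ratio shifted in an unknown direction, and primary-care costs shifted with it. Two people extracting charts might also apply the two sections differently.

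**Working it through.** **Step 1: do the texts really give two clocks?**

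- *Research Objectives.* Objective 1 ties function, pain and quality of life to a year from the initial consultation, as objective 2 does for workload. Yet Table 1 and section 2, Individual Health and Experience Outcomes, time those surveys from baseline and enrolment. The phrase is evidently a loose name for study entry in objective 1, and nothing makes it stricter in objective 2.
- *Duration of Treatment Period.* It speaks of process outcomes and does not name the visit outcome. Applying it to visits is an inference. It is a reasonable one, since the Implementation section lists EHR visits alongside process measures.
- *Health System Outcomes.* Initial and follow-up can describe types of visit inside the window. Pain of any duration was eligible, so the first visit of an episode is not a clean starting point for everyone.
- *Data Collection and Management.* The wording fixes the scope of extraction (all hip or knee primary care) and need not set a rival window.
- *Table 1.* As it reads here, provider encounters and EHR utilization are marked at 3 to 12 months only. Hip and knee management, also drawn from the EHR, is marked at baseline too. This leans towards enrolment without settling the matter.

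One year from consent throughout is thus an available reading. Including the earlier visit is also possible, so its loss is not certain.

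**Step 2: how far apart could the two counts be?**

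The documents give no visit rate, rate ratio or route share, so there is no plan figure to reproduce. Every input below is an assumption.

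- m0, m1: mean physician/NP visits in usual care and PT-led care with the pre-consent visit included
- s: share of each arm whose first visit came before consent and is not counted
- f: fraction of those PT-led visits made to a physician or NP (all of them are, in usual care)

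Rate ratio (RR) counted from consent = (m1 − s·f) / (m0 − s)

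With m0 = 2.5 and m1 = 1.5, the RR with the visit included is 1.5/2.5 = 0.60.

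| s | f = 1 | f = 0 |
|---|---|---|
| 10% | 1.4/2.4 = 0.58 | 1.5/2.4 = 0.63 |
| 30% | 1.2/2.2 = 0.55 | 1.5/2.2 = 0.68 |
| 50% | 1.0/2.0 = 0.50 | 1.5/2.0 = 0.75 |

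Setting the formula equal to m1/m0 gives f = m1/m0. With equal shares the two counts agree when f is 0.60; above that the RR falls and below it the RR rises.

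Other assumed inputs behave alike:

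- Means of 3 and 2 (RR 0.67), s = 30%: 1.7/2.7 = 0.63 to 2.0/2.7 = 0.74.
- Same means, f = 1, unequal shares: 1.5/2.8 = 0.54 (20% usual care, 50% PT-led) or 1.8/2.5 = 0.72 (50% and 20%).
- No difference (2.5 and 2.5), s = 30%: 2.2/2.2 = 1.00 at f = 1, and 2.35/2.2 = 1.07 at f = 0.5.

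**Step 3: what does the gap between the counts mean?**

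The formula treats the count that includes the early visit as the truth. That is only one of two sensible targets. Visits in the year after consent is equally well defined, and it matches the window for surveys, costs and quality-adjusted life years (QALYs). The table measures the distance between two targets, not the error of one.

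**The case for a change.** The strongest reply is that sites were randomized before patients were recruited. A pre-consent visit is therefore still post-randomization and can be affected by the model of care, and leaving it out discards part of the workload that the trial set out to study. The plan also recognises in-visit recruits when it defines timely access, so its silence elsewhere looks like an oversight. Whether the PT was first contact for the current episode, another of its measures, may itself require looking back before consent.

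Much of this stands. The plan states no start-date rule, and the arms could be affected unequally. It does not show that counting from consent is wrong. For an in-visit recruit the index visit was a condition of entry. Including it gives that person a guaranteed visit with almost no added person-time, so that count also depends on recruitment route. It also places a cost before the QALY year.

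Requiring its inclusion has a practical price too. Recruitment ended in November 2024 and the document is dated 20 November 2025, so most participants had reached the one-year extraction point. Charts might have to be reopened by research assistants who are not blinded, and consent would have to be shown to cover the earlier visit.

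**Conclusion.** No change to the plan is called for. What remains is a missing detail, the date on which EHR visit counting begins, which analysts can settle sensibly by using one date in both arms with the offset and costs to match. Whether that date admits the index visit is a fair trade-off. A statistician could count from consent and show the index visits as a sensitivity analysis, or do the reverse.

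The size is unknown and may be nil. The wide ranges need half of each arm to have an uncounted pre-consent visit, whereas the protocol presents in-visit identification as an addition to screening at booking. If the share were 10%, the illustrative RR of 0.60 would become 0.58 to 0.63. These figures rest wholly on assumed means, shares and first-contact fractions. The LEFS analysis and its sample size are untouched.
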